9.1.2 Site initiation visit

Before initiation of the clinical investigation, sponsor must be provided with key personnel signed and dated curriculum vitae, less than two years old and documentation of current qualifying training in the ISO14155 to verify their qualifications as research staff.

All clinical investigation sites will complete an initiation visit during which, full training on all aspects of the clinical investigation will be provided.

Training in use of the equipment used for measuring endpoints will be performed at sites.

9.1.3 Monitoring visit(s)

The sponsor shall determine the extent and nature of monitoring appropriately for the clinical investigation based on the risk assessment. The sponsor shall ensure, through oversight of the clinical investigation and timely adverse event reporting, that unanticipated adverse device effects are identified and investigated rapidly so that, where necessary, additional risk control measures can be implemented.

The site dedicated monitor is to ensure adherence to the clinical investigation plan, the safety of the subjects, accurate data recording on the e-CRFs and to monitor recruitment rates and adherence to follow-up schedules. During the clinical investigation, monitors shall check that appropriate written informed consents have been obtained. The principal investigator shall permit and assist the monitor to carry out verification of completed e-CRFs against data in the source documents.

The principal investigator can delegate tasks to his/her collaborators, however the roles and responsibilities as time period of involvement for each clinical site personnel must be documented on the Site Personnel signature and Delegation list as well as training received before getting involved with the clinical investigation, must be documented in the Clinical Investigation Training Log.

The monitor shall inform the sponsor about any problems relating to facilities, technical equipment or medical staff at the clinical investigation site. The monitor shall also be responsible for notifying such deficiencies in writing to the principal investigator and convene with the clinical investigation site personnel appropriate and timely corrective actions.

The sponsor, or delegate, will provide clinical monitoring, including review of eCRF with verification to the source documentation.

The monitor shall make written reports to the sponsor, including documentation of any deviations after each visit and provide written follow up action items if any, to the principal investigator and/or clinical investigation site personnel.

Periodic monitoring visits (remote or on-site) will be performed as soon as reasonable possible, after the site has enrolled the first subject in the investigation. A final monitoring visit will be performed after all subjects on site have completed the investigation.

9.2 Remote monitoring

Remote (source data verification) and/or centralized (data review) monitoring is carried out by sponsor personnel or representatives (e.g., data management personnel, statisticians, or clinical monitors) at a

location other than the site(s) at which the clinical investigation is being conducted (evaluation without visiting the investigation site). Remote monitoring processes can provide many of the capabilities of on-site monitoring as well as additional capabilities.

In addition to onsite monitoring visits, remote monitoring of the data entered in the eCRF system could be used to achieve the following:

- Conduct activities such as: standard checks of range, consistency, and completeness of data and checks for unusual distribution of data, such as too little variance
- Special attention will be given in case of frequent data anomalies or errors, protocol deviations or excessive dropouts.
- Augment on-site monitoring by performing monitoring activities that can only be accomplished using centralized processes (e.g., statistical analyses to identify data trends not easily detected by on-site monitoring)
- Monitor data quality through routine review of submitted data in real-time to identify missing data, inconsistent data, data outliers, and potential protocol deviations that may be indicative of systemic and/or significant errors in data collection and reporting at the site
- Verify source data remotely, provided that both source data and CRFs can be accessed remotely
- Conduct aggregate statistical analyses of study data to identify subject data that are outliers relative to others and to evaluate individual subject data for plausibility and completeness
- Conduct analyses of site characteristics, performance metrics (e.g., high screen failure rates, high frequency of eligibility deviations, and delays in reporting data), and clinical data to identify early on corrective actions needed for characteristics correlated with poor performance or noncompliance

9.3 Source data verification

Source data is all information in original records, certified copies of original records of clinical findings, observations, or other activities in the clinical investigation, necessary for the reconstruction and evaluation of the clinical investigation. This includes source data initially recorded in an electronic format.

All documents and data related to the clinical investigation handled by site personnel, shall be produced and maintained in a way that assures reliability, integrity, control and traceability, and shall be appropriately stored to provide a complete history.

The Principal Investigator shall assure the accuracy, attribution, completeness, legibility and timeliness of the data reported to the sponsor in the eCRFs and in all required reports. All printed copies of electronic source documents shall be certified, as indicated by a dated signature by the investigational site personnel at the time the document is printed. Special requirements should be applied to the capture, review and retention of electronic source data, to ensure reliability, quality, integrity and traceability.

The data reported in the eCRFs shall be derived from source documents and be consistent with these source documents, and any discrepancies shall be explained in writing. The eCRF can serve as the source document and this must be documented on the Source Data Specification Form. The Source Data Specification Form must be completed at the initiation visit detailing the location of the source data for each data point agreed upon by the principal investigator.

10 Statistical considerations

10.1 Statistical design, method, and analytical procedures

The primary objective will be evaluated by analysing the primary endpoint.

Baseline assessments and endpoints will be reported by descriptive statistics and/or listed.

Summaries will be presented by device i.e., investigational or comparator device and if relevant, by other grouping variables.

Descriptive statistics for continuous variables are presented with N, Mean, SD (standard deviation), Median, Min and Max, where N denotes the number of subjects contributing with non-missing data. For discrete variables, descriptive statistics are presented with N and percentage, where percentage is based on the total number of subjects/observations with non-missing data.

All statistical analysis will be performed with SAS version 9.4/Enterprise Guide version 7.1.

10.2 Definition of analysis populations

Screening Failures (SF), Intention to Treat (ITT), Full Analysis Set (FAS), Safety and Per Protocol (PP) analysis set will be defined at a formal data review meeting prior to database lock. As a minimum, the data manager, the clinical manager, and the statistician will be involved in the classification of subjects.

Subjects not adhering to inclusion and/or exclusion criteria are considered screening failures (SF) and are not included and randomised.

- The Safety population will constitute all subjects included i.e. subjects who have given informed consent and fulfils the in- and/or exclusion criteria.
- The ITT population will constitute all randomised subjects.
- The full analysis set is a modified ITT population i.e., a sub-population of the ITT population, and will constitute all randomised subjects, who have been exposed to at least one device, with at least one endpoint recorded (data non-missing).
- The PP is a sub-population of the full analysis set where all subjects have received treatment as per protocol.

Individual endpoints/data points may be excluded from the analysis, even though the corresponding subject belongs to any of the pre-defined populations. Exclusion of subjects or data points must be documented.

All statistical analysis and test of hypothesis will be based on the full analysis set, and in addition, primary endpoint will also be analysed in the PP population, whereas adverse events and device deficiencies will be assessed in the safety population.

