5.8 Randomisation Procedure

All subjects that have given informed consent and meet the inclusion and exclusion criteria will be randomised.

This investigation involves two treatments, the investigational device, and the comparator devices

The Rave RTSM™ is a validated randomization solution, that will be used for the randomization in this investigation. A centralized randomization will be implemented, in which, participants are to be randomly assigned to two intervention sequences in block sizes of 8.

For technical reasons, to ensure correct randomization in an equal split between treatment arms, the two treatment arms are technically implemented as illustrated below.

Treatment A: Investigational Device × Comparator 1 (SpeediCath Compact Eve) (25%)

Treatment B: Investigational Device × Comparator 2 (SpeediCath Compact Plus Female) (25%)

Treatment C: Comparator 1 (SpeediCath Compact Eve) × Investigational Device (25%)

Treatment D: Comparator 2 (SpeediCath Compact Plus Female) × Investigational Device (25%)

Randomisation will be 2:1:1 (Investigational device: Comparator: SpeediCath Compact Eve: SpeediCath Compact Plus Female)

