6.1.2 Exclusion criteria

For an eligible subject, all exclusion criteria must be answered "no":

Exclusion criteria	Justification for exclusion criteria
1. Is participating in any other clinical study during this investigation	To eliminate uncertainty whether any Adverse Events (AE's) or Serious Adverse Events (SAE's) occurring during the investigation relate to the usage of the herein tested devices. Also, to eliminate unintentional effect from other devices/medicines on the investigation's data.
2. Has previously participated in this study	To ensure integrity of results.
3. Has symptoms of urinary tract infection at time of inclusion, as judged by the investigator (if the	To ensure subject safety and integrity of results.

patient recovers within the recruitment period, a second inclusion is allowed, under a different subject id)	
4. Is an individual with a history of - suspected to be – or showing signs of producing an excessive amount of mucus or large/clustered sediments or debris	To ensure subject safety and integrity of results.
5. Has any known allergies towards ingredients in the investigational device	To ensure subject safety and integrity of results.
6. Is pregnant	Even though the ingredients and the recipes have been approved for human beings, their effect on embryos, foetuses and infants are unknown
7. Is breastfeeding	Even though the ingredients and the recipes have been approved for human beings, their effect on embryos, foetuses and infants are unknown

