6.4 Screening Failures and Drop-Outs

Subjects that have signed the informed consent form but fail to comply with inclusion or exclusion criteria are considered "screening failures" up until randomisation. After randomisation subjects who fail to comply with inclusion or exclusion criteria will be withdrawn from the study and considered "drop-outs"

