7.2 Clinical investigation-related procedures

Visit 0 (V0) – Screening:

- Information about investigation, screening and review of Informed Consent Form/Subject Information Form
- Scheduling Baseline Visit (V1) unless performed the same day as Screening Visit (V0)
- Register the potential subject on the Pre-screening Log if not already registered

Visit 1 (V1) – Inclusion, Baseline and introduction to T1:

NB! The subject should not have changed their medication the last 24 hours before V1. If subjects show symptoms of UTI (assessed by investigator), they must be rescheduled.

- Introduction to the investigation reviewed and confirmed
- Informed Consent signed
- Enrolment in the investigation and allocation of subject number
- Check of in- and exclusion criteria
- For female subjects of childbearing potential: urine pregnancy dipstick
- Collect Baseline information:
 - Age [years]
 - Height [cm]
 - Weight [kg]
 - When did you start using a catheter (YEAR + MONTH (if known))
 - Average number of catheters used per day [number]
 - Current primary product
 - Coloplast: SpeediCath Compact Female, SpeediCath Compact Female Plus, SpeediCath Compact Eve
 - Wellspect: Lofric Sense, Lofric Elle
 - Hollister: Infyna Chic, Vapro Pocket
 - B. Braun: Actreen Mini
 - Bard: Hydrosil Rose, Hydrosil GO, Magic3Go
 - Convatec: GentleCath Air Female
 - Curan: Curan Lady, Curan Twist
 - Other (text)
 - Current product size
 - CH12
 - CH14
 - Position most frequently used in catheterisation
 - Sitting
 - Laying
 - Standing
 - Other (text)
 - Urethral sensation
 - Normal
 - Impaired
 - None

- Hypersensitive
- Reason for using intermittent catheterisation
 - Spinal cord injury
 - Multiple sclerosis
 - Spina Bifida
 - Others (as text)
- Neurogenic/Non-neurogenic
- Body mobility / ambulation
 - Walking
 - Walking with difficulty/aids
 - Using a wheelchair
 - Confined to bed
- How is your dominant hand?
 - Right-handed
 - Left-handed
 - Mixed or cross-dominant (i.e., changes according to task)
 - Ambidextrous (i.e., equal ability in both hands)
- How would you describe the level of dexterity of your hands?
 - Left hand
 - Normal dexterity
 - Reduced dexterity
 - Greatly reduced dexterity
 - Don't know
 - Right hand
 - Normal dexterity
 - Reduced dexterity
 - Greatly reduced dexterity
 - Don't know
- Concomitant medication related to urinary function (assessed by principal investigator) and pain management
- Relevant medical history (assessed by the investigator)
- Randomization

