- Introduction to 1st randomly assigned product, including IFU.
- Self-catheterisation (with 1st randomly assigned product)
- Catheterisation position noted [Sitting/standing]
- Catheter used for catheterisation noted [investigational product/comparator, including product size (CH12/CH14)]
- Catheter handed out for the first test period is noted [investigational product/comparator, including product size (CH12/CH14)]
- Scheduling Visit (V2), 14 days (+/-3 days) days after Baseline Visit (V1)
- Complete eCRF

Test Period 1 (T1):

The two weeks of home-use with the first randomly assigned product according to an individual usage regime. No data will be collected during the home period.

Visit 2 (V2) – Catheterisation, follow-up and introduction to T2

The subject should not have changed their medication the last 24 hours before V2 or show symptoms of UTI (assessed by investigator). If signs of UTI, they must be rescheduled and registration of AE.

- Ask for change in relevant medical history since last visit.
- Review of Adverse events/Serious adverse events/Adverse device events, Device deficiencies and Protocol Deviations
- Review of changes in concomitant medication
- Assessment on user perception for Test Period 1.

HCP-Catheterisation:

- Pre-catheterisation volume [mL] measured in triplicate with a bladder scanner. All three measurements must be above 150 ml to proceed. If not subject is asked to intake fluid and wait until bladder volume is ≥ 150 ml.
- Catheterisation with the 1st randomly assigned product used in T1 will be performed by HCP. NB! HCP should wait for 3 sec. when suspicion of flow-stop before rotating catheter to make it more clear on the profile from the databox.
- Catheter used for catheterisation [investigational product/comparator, including product size (CH12/CH14)], position [Sitting/standing], and time for start of catheterisation is noted.
- Urine volume at 1st flow stop [g] and post catheterisation [g] is noted.
- Number of flow stops is noted.
- All assessments pertaining to performance, including catheterisation profile, will be recorded at the catheterisation.
- Residual volume [mL] will be measured in triplicate with bladder scanner after catheterisation is completed.
- After first catheterisation subjects will be asked to intake fluid and wait in the waiting room to ensure there is urine in the bladder before the second catheterisation.

Self-Catheterisation:

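### Section 10.2 defines the Safety population by eligibility rather than device use, and its screening-failure sentence conflicts with section 6.4

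*Combined protocol and SAP*

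**What the plan says.** **Safety set.** Section 10.2 defines it by consent and eligibility: "The Safety population will constitute all subjects included i.e. subjects who have given informed consent and fulfils the in- and/or exclusion criteria". The same section assigns adverse events and device deficiencies to this set and to no other.

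**Screening failures.** The sentence just before that definition reads: "Subjects not adhering to inclusion and/or exclusion criteria are considered screening failures (SF) and are not included and randomised". Section 5.8 describes the same gate: "All subjects that have given informed consent and meet the inclusion and exclusion criteria will be randomised".

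**Failures found after randomisation.** Section 6.4 confines the screening-failure label to the time before randomisation and then adds: "After randomisation subjects who fail to comply with inclusion or exclusion criteria will be withdrawn from the study and considered" drop-outs.

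**Other sets.** For ITT, 10.2 says: "The ITT population will constitute all randomised subjects". The full analysis set is the part of ITT that used at least one device and has at least one recorded endpoint. This is the only place in 10.2 where device use is a condition.

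**Meaning of *included*.** Table 1 in section 6.2.1 treats a subject as included once the consent form is signed. Section 10.2 ties the word to consent plus fulfilled criteria.

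**The concern.** A safety set should hold the people who were exposed to the products. Here membership turns on eligibility, and the definition is sound only if no ineligible subject is ever randomised. Section 10.2 assumes this. Section 6.4 does not, because it sets out what happens when such a subject is found.

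Safety is one of the secondary objectives (section 3.1) and the number of adverse events is a secondary endpoint (section 5.3). The investigational device is not CE-marked. At stake is whether a subject who used a study catheter, and was afterwards found not to meet a criterion, keeps her place in the safety summaries by device: her events in the count and herself in the denominator.

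**Working it through.** The plan gives no figure to reproduce on this point. The check is a comparison of the sections, followed by a head count.

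**Step 1: can an ineligible subject be randomised?** Section 10.2 says no ("Subjects not adhering to inclusion and/or exclusion criteria are considered screening failures (SF) and are not included and randomised"). Section 6.4 says it can happen and names a separate class for it ("After randomisation subjects who fail to comply with inclusion or exclusion criteria will be withdrawn from the study and considered" drop-outs). Both are current text, so they conflict.

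**Step 2: will she have been exposed?** Section 7.2 lists the Visit 1 steps in order. "Check of in- and exclusion criteria" comes first, then baseline information, then randomisation, then introduction to the product, then "Self-catheterisation (with 1st randomly assigned product"). Catheters for the first test period are handed out at the same visit. A subject wrongly passed at the check will therefore normally have used a study catheter before the error is found.

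**Step 3: which sets does she belong to?** Applying the rules of 10.2 as written:

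| Set | Condition in 10.2 | Exposed subject found ineligible after randomisation |
|---|---|---|
| ITT | randomised | in |
| Full analysis set | randomised, used a device, has an endpoint | in, if an endpoint was recorded |
| Safety | consented and meets the criteria | out on the literal reading |

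On that reading she can contribute to the performance results but not to the safety results.

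**Step 4: is the literal reading the only one?** No. If *included* has the meaning of Table 1 in 6.2.1 (consent signed), or means that the subject was passed at the Visit 1 check, she stays in. Against this, the explanatory clause in "The Safety population will constitute all subjects included i.e. subjects who have given informed consent and fulfils the in- and/or exclusion criteria" adds fulfilled criteria to consent, and a subject wrongly passed never fulfilled them. The text does not settle the matter.

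**Step 5: size.** Section 10.7 plans to randomise at least 72 subjects. The documents give no rate of ineligibility found after randomisation, so the number *k* of such subjects is an assumption, as is exposure of all 72. The share of exposed subjects outside the Safety set is *k*/72:

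| *k* (assumed) | Safety set | Share left out |
|---|---|---|
| 0 | 72 | 0% |
| 1 | 72 − 1 = 71 | 1/72 = 1.4% |
| 2 | 72 − 2 = 70 | 2/72 = 2.8% |
| 4 | 72 − 4 = 68 | 4/72 = 5.6% |
| 7 | 72 − 7 = 65 | 7/72 = 9.7% |

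These are head counts. They do not measure lost events.

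**The case against.** The best defence is that the sections can be read together. The screening-failure sentence in 10.2 would then describe only the period before randomisation, and the Safety set would mean everyone who passed the Visit 1 check and was enrolled. This is a fair reading and it stands as a possibility. It does not make the definition safe, because the words about fulfilled criteria point the other way.

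A second defence is that subjects are classified at a data review meeting before database lock and that exclusions must be documented. Both are true. The meeting would still have to apply 10.2 and 6.4, which disagree about exactly this subject.

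Third, little can be lost. Investigators assess and report events under section 18 regardless of analysis set, section 20 requires the report to evaluate all collected data, and the safety analysis is listing and summary without a test. This stands in full and limits the weight of the point.

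A reader might also infer that two further groups are misplaced. One is the subject who was eligible at Visit 1 and later stops meeting a criterion, for example "Is participating in any other clinical study during this investigation". Section 10.2 names no time point, but several other criteria carry their own, and such a subject arguably stays in the Safety set. The other is the eligible subject who never uses a study catheter. She would count in the Safety set, but randomisation and first use belong to the same visit, so the case is close to hypothetical. Neither group carries the point.

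**Conclusion.** The point holds as a defect of definition. Section 10.2 sets no exposure condition for the Safety population, and its statement that ineligible subjects are not randomised contradicts 6.4. On the literal reading, an exposed subject found ineligible after randomisation falls outside the only set used for adverse events and device deficiencies. On another reading she stays in. The supported conclusion is that her place is not secured.

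The number of such subjects cannot be derived from the documents and may be zero. Each is 1.4% of the planned 72, assuming all are exposed. The primary analysis uses the full analysis set and does not change.

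A reader might go further and infer that safety events will be concealed or go unreported. The documents do not support this, given section 18 and the duty to document exclusions. The change is worth making because it is nearly free and removes a judgement that would otherwise be made after the data are in.

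**What to change.** In 10.2, define the Safety population as all subjects who used at least one study catheter, investigational or comparator, regardless of any later finding on eligibility. Reconcile the screening-failure sentence in 10.2 with 6.4, so that both sections agree on the status of a randomised subject who does not meet the criteria. Give *included* one meaning across 10.2 and Table 1 of 6.2.1. None of this takes a position on the withdrawal rule itself.

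The cost is one definition and two aligned wordings. Membership can be read from data already planned, since the catheter used at Visit 1 is recorded (sections 5.5 and 7.2).

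The change concerns who is in the set. How each event is attributed to a device is a separate matter and is not part of this fix. In particular, the visit at which an event is reviewed should not be taken to identify the device in use: at Visit 2, section 7.2 lists the adverse event review before that visit's catheterisations with the first product, so an event following them could surface only at Visit 3.
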